5.2 EXCLUSION CRITERIA

Exclusion Criteria

For Aims 1 and 2: Patients will be excluded for: 1. exclusive use of non-cigarette tobacco or nicotine products, including e-cigarettes; 2. current use of NRT, VAR, or bupropion (defined as use of medication in prior 7 days); 3. self-report or urine testing confirming pregnancy, nursing, or trying to conceive; 4. Life-threatening or unstable medical, surgical, or psychiatric condition; 5. inability to provide at least 1 collateral contact for a friend or family member; 6. living out-of-state; or 7. inability to read or understand English or Spanish.

For Aim 3: Participants will be excluded for 1) less than 18 years of age and 2) NOT employed at the HIV clinic.

Enrollment Restrictions Based Upon Gender, Pregnancy, Childbearing Potential, or Race

Yes

5.3 LIFESTYLE CONSIDERATIONS

If the participant is a woman and wants to take part of the study, they need to use birth control while they are participating in the study.

5.4 SCREEN FAILURES

People who are pre-screened are assigned a study ID will be tracked so we know who is eligible and ineligible.

5.5 STRATEGIES FOR RECRUITMENT AND RETENTION

How Participants Will Be Identified

For Aims 1 and 2, potential participants will be identified by chart review or via data reports filtered on eligibility criteria, in advance of the clinic. We will develop recruitment flyers specific to each site. Potential participants may be referred to the study team by a clinic provider or staff member. In addition, eligible patients may be informed about the study by messaging via medical record as applicable at a given site (e.g., Epic MyChart). Patients may also self-refer after hearing about the study from a public service announcement in the clinic waiting room.

For Aim 3, all clinicians, staff, clinical leadership, social workers, psychologists, and care coordinators employed at the participating site will be invited to complete the brief surveys pre- and post- trial intervention.

Who Will Initially Approach Potential Participants

Study Personnel

How Research Will Be Introduced to Participants

Potentially eligible patients may be recruited via multiple pathways:

1. Direct referral by clinic provider or staff;
2. Self-referral based on recruitment flyer, peer, or otherwise;
3. Proactive, opt-out recruitment based on electronic medical record review, followed by mailed letter and, if the patient does not opt out of being called, research team outreach; and/or
4. Messaging through the secure medical record with invitation to participate as available at a given site and per site policies.
5. Self-referral via a public service announcement on video monitors in the clinic waiting room.

Individuals who meet inclusion and exclusion criteria and provide written consent to participate will have baseline assessments performed, and then will be randomized 1:1 to either NRT or NRT+CM.

For the Yale New Haven Hospital site only (Aims 1 and 2):

To assist in recruitment, the Yale Clinical Center for Investigation (YCCI) will help to identify potential eligible participants. The YCCI team will mail recruitment letters and post social media advertisements. In addition, they will send announcements through the Help Us Discover database, which contains several thousand individuals who volunteer for clinical research. Additionally, they will send messages through the secure messaging system through the medical record (MyChart via Epic) for those patients who have opted in to being contacted for clinical research studies.

For the SUNY/Downstate site only (Aims 1 and 2):

A public service announcement (PSA) will play on a loop on video monitors in clinic waiting areas. The PSA will give a brief description of the study and will include a contact telephone number for patients to contact the study team.

For Aim 3, all clinicians, staff, clinical leadership, social workers, psychologists, and care coordinators employed at the participating site will be invited to complete the brief surveys pre- and post- trial intervention. The pre-trial survey will occur within the first 3 months of the RCT launch; the post-trial survey will occur within the last three months of the RCT completion.

6 STUDY INTERVENTION

6.1 STUDY INTERVENTION(S) ADMINISTRATION

6.1.1 STUDY INTERVENTION DESCRIPTION

Refer to these documents that were submitted and approved by the IRB:

Nicorette insert

Nicorette lozenge insert

Nicorette patch insert

Varenicline (Chantix) insert

Bupropion

6.1.2 DOSING AND ADMINISTRATION

6.2 PREPARATION/HANDLING/STORAGE/ACCOUNTABILITY

6.2.1 ACQUISITION AND ACCOUNTABILITY

The clinical pharmacist during the study visit will control the product (based on the images of the drugs that we submitted and were approved by the IRB) based on how much the participant smokes:

Prescribe dosing of patch based on patient's level of tobacco use

5-9 cigarettes per day: 14mg patch

>10 cigarettes per day: 21mg patch

Prescribe short-acting NRT based on timing of first daily cigarette:

First cigarette is within 30 minutes of waking: 4mg

First cigarette is after 30 minutes of waking: 2mg

Prescribe varenicline as follows:

Days 1-3: 0.5 mg once per day

Days 4-7: 0.5 mg twice per day

Day 8 until end of treatment: 1 mg twice per day

Prescribe bupropion as follows:

Days 1-3: 150mg per day

Day 4 until end of treatment: 150mg twice per day

6.2.2 FORMULATION, APPEARANCE, PACKAGING, AND LABELING

Refer to sections 6.1.1 and 6.2.1

6.2.3 PRODUCT STORAGE AND STABILITY

N/A

6.2.4 PREPARATION

N/A

6.3 MEASURES TO MINIMIZE BIAS: RANDOMIZATION AND BLINDING

Randomization is conducted through REDCap, clinical trials data management system. Participants, clinical pharmacists, nor research coordinators are blinded to treatment condition.

6.4 STUDY INTERVENTION COMPLIANCE

Study intervention compliance will be recorded in REDCap based on self-reported information of medication and compliance will be measured based on participants showing up to pharmacy visits which will also be recorded on REDCap.

6.5 CONCOMITANT THERAPY

6.5.1 RESCUE MEDICINE

N/A

7 STUDY INTERVENTION DISCONTINUATION AND PARTICIPANT DISCONTINUATION/WITHDRAWAL

7.1 DISCONTINUATION OF STUDY INTERVENTION

The intervention may be discontinued if a participant has adverse effects from the prescribed medications. However, the participant will remain in the study for follow-up assessments.

7.2 PARTICIPANT DISCONTINUATION/WITHDRAWAL FROM THE STUDY

Anticipated Circumstances of Subject Withdrawal

Participants may be withdrawn from the research without their consent if they are deemed ineligible for the study. Participants may also be withdrawn from the research if they have experienced serious or related adverse events. If any participant asks to withdraw from the study, they will be notified that medical record data collection will continue, but any interventional procedures may cease. If a participant asks for complete withdrawal from the study, he or she must do so by written notification to the site-PI.

Procedures for Subjects to Request Withdrawal

If any participant asks to withdraw from the study, they will be notified that medical record data collection will continue, but any interventional procedures may cease. If a participant asks for complete withdrawal from the study, they must do so by written notification to the site PI.

Procedures for Investigator to Withdraw Subjects

Participants may be withdrawn from the research without their consent if they are deemed ineligible for the study. Participants may also be withdrawn from the research if they have experienced serious or related adverse events. If participants are lost to follow-up, they will not be withdrawn. We will try to continue to get assessments through 24 weeks and complete data collection via the electronic medical record, unless consent is withdrawn in writing.

7.3 LOST TO FOLLOW-UP

Site staff will make every effort to contact study participants, including calling and texting alternate telephone numbers using the Zoom Phone application. In addition, site staff will try to meet participants when they are in clinic for their regular visits with their providers. If they are unable to reach a participant, a letter will be sent to their last known mailing address. Participants should not be considered lost to follow up until 6 months after the 24 weeks have elapsed.

8 STUDY ASSESSMENTS AND PROCEDURES

8.1 EFFICACY ASSESSMENTS

We will have participants do labs to study the longitudinal impact of smoking on the Veterans Aging Cohort Study (VACS) Index, a validated measure that predicts morbidity and mortality risk. Based on routinely collected lab tests (CD4 count, HIV viral load, hemoglobin, AST, ALT, platelets, creatinine, and HCV status, albumin, white blood cell count), the VACS Index correlates with measures of inflammation, microbial translocation, and impaired T cell activation known to be elevated with HIV and smoking. Exhaled carbon monoxide testing will also be collected to confirm abstinence.

8.2 SAFETY AND OTHER ASSESSMENTS

In this study we will collect lab work from participants that includes their physical examinations, CD4 count, viral load, diagnostic labs (metabolic panel) and eCO.

8.3 ADVERSE EVENTS AND SERIOUS ADVERSE EVENTS

8.3.1 DEFINITION OF ADVERSE EVENTS (AE)

Grading System to Evaluate Adverse Events

The following scale will be used in grading the severity of adverse events noted during the study:

1. Mild adverse event
2. Moderate adverse event.

3. Severe unanticipated adverse event resulting inpatient hospitalization or prolongation of existing hospitalization, a persistent or significant disability/incapacity, or a congenital anomaly/birth defect.
4. Life-threatening adverse event
5. Fatal adverse event

8.3.2 DEFINITION OF SERIOUS ADVERSE EVENTS (SAE)

An adverse event (AE) or suspected adverse reaction is considered "serious" if, in the view of either the investigator or sponsor, it results in any of the following outcomes: death, a life-threatening adverse event, inpatient hospitalization or prolongation of existing hospitalization, a persistent or significant incapacity or substantial disruption of the ability to conduct normal life functions, or a congenital anomaly/birth defect. Important medical events that may not result in death, be life-threatening, or require hospitalization may be considered serious when, based upon appropriate medical judgment, they may jeopardize the participant and may require medical or surgical intervention to prevent one of the outcomes listed in this definition. Examples of such medical events include allergic bronchospasm requiring intensive treatment in an emergency room or at home, blood dyscrasias or convulsions that do not result in inpatient hospitalization, or the development of drug dependency or drug abuse.

8.3.3 CLASSIFICATION OF AN ADVERSE EVENT

8.3.3.1 SEVERITY OF EVENT

- **Mild** – Events require minimal or no treatment and do not interfere with the participant's daily activities.
- **Moderate** – Events result in a low level of inconvenience or concern with the therapeutic measures. Moderate events may cause some interference with functioning.
- **Severe** – Events interrupt a participant's usual daily activity and may require systemic drug therapy or other treatment. Severe events are usually potentially life-threatening or incapacitating. Of note, the term "severe" does not necessarily equate to "serious".]

Grading System to Evaluate Adverse Events

The following scale will be used in grading the severity of adverse events noted during the study:

1. Mild adverse event: Events require minimal or no treatment and do not interfere with the participant's daily activities.
2. Moderate adverse event: Events result in a low level of inconvenience or concern with the therapeutic measures. Moderate events may cause some interference with functioning.
3. Severe unanticipated adverse event: resulting inpatient hospitalization or prolongation of existing hospitalization, a persistent or significant disability/incapacity, or a congenital anomaly/birth defect.
4. Life-threatening adverse event
5. Fatal adverse event

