9.4.3 SAFETY ANALYSES

To assess safety of treatment interventions, we will describe adverse events by treatment group and compare by treatment group. We will additionally examine self-reported bothersome symptoms based on response to the HIV Symptom Index, numbers of hospitalizations and ED visits overall and by treatment group.

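### Grade 3 of the adverse event scale conflicts with the definition of severe in the same section, and some severe events fit no grade

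*Combined protocol and SAP*

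**What the plan says.** Section 8.3.3.1 (Severity of Event) describes severity twice.

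- **Three-level list.** Mild, moderate and severe are defined by intensity and effect on function. For severe: "Events interrupt a participant's usual daily activity and may require systemic drug therapy or other treatment". The list adds that "Severe events are usually potentially life-threatening or incapacitating", and notes that severe need not mean serious.
- **Five-grade scale.** It is introduced with "The following scale will be used in grading the severity of adverse events noted during the study". Grades 1 and 2 repeat the mild and moderate definitions. Grade 3 does not repeat the severe definition. It reads: "Severe unanticipated adverse event: resulting inpatient hospitalization or prolongation of existing hospitalization", and goes on to list lasting disability or incapacity and birth defect as further outcomes. Grades 4 and 5 are life-threatening and fatal.

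Section 8.3.1 gives the same five grades, and its grade 3 is again a "Severe unanticipated adverse event resulting inpatient hospitalization or prolongation of existing hospitalization", with the same further outcomes.

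Two other attributes have their own sections. Section 8.3.2 defines a serious adverse event by outcomes that include hospitalization, lasting incapacity and birth defect. Section 8.3.3.3 makes expectedness a separate judgement by the site investigator, based on whether the nature, severity or frequency of the event agrees with the risk information already given.

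**The concern.** A severity grade should say how intense an event was. As written, grade 3 also requires that the event was unanticipated and that it had an outcome from the seriousness list. Those are different questions, and the protocol answers them elsewhere. The section also contradicts itself: it separates severe from serious, then defines the severe grade by seriousness outcomes.

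Two stated uses of severity are exposed. Section 8.3.4 puts the clinician's severity assessment on the case report form and asks for changes in severity to be documented, so that time spent at each level can be assessed. Section 8.3.5 has the principal investigators weigh the frequency and severity of adverse events when deciding whether the protocol or consent form needs changing. If one event can defensibly receive different grades, both uses become less reliable. Section 1.1 names three enrolling sites, and section 6.3 says that participants, pharmacists and coordinators know the assigned treatment. An ambiguous criterion therefore leaves room for grading to vary by site or with knowledge of the arm.

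**Working it through.** The plan gives no figure on this point, so there is nothing to compute. The check is to set the definitions side by side and ask which grade each kind of event can receive.

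**Conditions under the literal wording**

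- Grade 2 (8.3.3.1): low-level inconvenience or concern, with at most partial interference with function.
- Grade 3 (8.3.1 and 8.3.3.1): unanticipated, and with hospitalization or its prolongation, lasting disability or incapacity, or a birth defect.
- Grades 4 and 5: life-threatening or fatal, with no condition on expectedness.

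**Events tested**

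| Event | Grade 2? | Grade 3? | Grade 4 or 5? | Result |
|---|---|---|---|---|
| Severe, anticipated, hospitalized, not life-threatening | No, exceeds it | No, not unanticipated | No | No grade |
| Severe, unanticipated, systemic treatment at home, no listed outcome | No, exceeds it | No, outcome missing | No | No grade |
| Convulsion without admission (an example of a possible serious event in 8.3.2), not life-threatening or disabling | No, exceeds it | No, outcome missing | No | No grade |
| Unanticipated, not hospitalized, lasting disability or birth defect | No | Yes | No | Grade 3 |
| Life-threatening or fatal, anticipated or not | No | Not needed | Yes | Grade 4 or 5 |

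The first three rows show the gap. The last two show its limits: lack of hospitalization alone does not put an event in the gap, and expectedness is irrelevant once an event is life-threatening or fatal.

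**Does the three-level list fill the gap?** It would call the first three events severe, but nothing maps that list to the five grades, and the five-grade scale is the one stated to be used. The list also describes severe events as usually potentially life-threatening, which overlaps grade 4. A site could reach grade 2 (grade 3 conditions not met), grade 3 (the event is severe by the list) or grade 4 (potentially life-threatening) for the same event.

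**Is it an isolated slip?** The same grade 3 wording stands in both 8.3.1 and 8.3.3.1. Grades 1 and 2 in 8.3.3.1 carry over the list definitions, and only the severe definition was not carried over.

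**The case against.** The strongest reply is that this is a drafting inconsistency with little consequence. The surrounding text has a stray closing bracket, and section 8.3.3.2 leaves two alternative causality scales joined by an unresolved OR, so unedited template text is a plausible cause. No stated safety action depends on the grade. Serious events are identified under 8.3.2 and reported under 8.3.6 whether related or not. Unanticipated problems have their own criteria and timelines in 8.4. Withdrawal under 7.2 refers to serious or related events, and the monitoring board in 10.1.6 works under its own charter. All of that stands and limits the consequence. It does not remove the conflict, because the scale is a stated rule and severity is both recorded and reviewed.

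A reader might infer more than the documents support:

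- *Listed drug effects are always expected, so they can never be grade 3.* Section 8.3.3.3 lets an event be unexpected in severity or frequency as well as nature. An unusually severe case of a listed effect could qualify, so a grade 3 count of zero for those effects does not follow. The protocol also never says whether unanticipated in the scale means unexpected in the sense of 8.3.3.3; section 8.4.1 uses the word for a different concept.
- *The scale systematically grades too low.* Nothing sends ungraded events to grade 2. The supportable statement is inconsistency, with no fixed direction.
- *The comparison of arms is distorted.* Section 9.4.3 says "we will describe adverse events by treatment group and compare by treatment group" and does not mention grade. Its hospitalization, emergency department and symptom summaries do not use the scale.

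**Conclusion.** The point holds in a limited form. Section 8.3.3.1 gives two conflicting meanings of severe, and the operative scale there and in 8.3.1 has a gap: events that are severe, neither life-threatening nor fatal, and either anticipated or without hospitalization, lasting disability or birth defect. Such events have no valid grade.

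The consequence is inconsistent severity data on the case report form and a less reliable basis for the principal investigators' review. The identification and reporting of serious events, and the efficacy analyses, are untouched. The size cannot be put as a number, because the documents report no adverse event counts or grades.

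The conclusion assumes that the five-grade scale is applied as worded and that no document outside this protocol, such as a manual of procedures, maps the two lists. It holds whichever meaning of unanticipated was intended, because either one excludes some severe events and the outcome condition excludes others. It should be corrected, but it does not threaten the trial's main results.

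**What to change.** 1. In 8.3.1 and 8.3.3.1, define grade 3 by the severe text already in the three-level list, and delete both the word unanticipated and the outcome wording.
2. State how grade 3 differs from grade 4, since the severe text itself refers to potentially life-threatening events.
3. Keep seriousness (8.3.2) and expectedness (8.3.3.3) as separate attributes, each recorded in its own right.
4. Re-check events already graded 2, 3 or 4 against the revised wording.

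The cost is a wording amendment to two sections and the re-check of recorded events. The protocol already contains the severity text needed, and no analysis or clinical management rule has to change.

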8.3.3.2 RELATIONSHIP TO STUDY INTERVENTION

The degree of certainty about causality will be graded using the categories below. In a clinical trial, the study product must always be suspect.

- **Related** – The AE is known to occur with the study intervention, there is a reasonable possibility that the study intervention caused the AE, or there is a temporal relationship between the study intervention and event. Reasonable possibility means that there is evidence to suggest a causal relationship between the study intervention and the AE.
- **Not Related** – There is not a reasonable possibility that the administration of the study intervention caused the event, there is no temporal relationship between the study intervention and event onset, or an alternate etiology has been established.

OR

- **Definitely Related** – There is clear evidence to suggest a causal relationship, and other possible contributing factors can be ruled out. The clinical event, including an abnormal laboratory test result, occurs in a plausible time relationship to study intervention administration and cannot be explained by concurrent disease or other drugs or chemicals. The response to withdrawal of the study intervention (dechallenge) should be clinically plausible. The event must be pharmacologically or phenomenologically definitive, with use of a satisfactory rechallenge procedure if necessary.
- **Probably Related** – There is evidence to suggest a causal relationship, and the influence of other factors is unlikely. The clinical event, including an abnormal laboratory test result, occurs within a reasonable time after administration of the study intervention, is unlikely to be attributed to concurrent disease or other drugs or chemicals, and follows a clinically reasonable response on withdrawal (dechallenge). Rechallenge information is not required to fulfill this definition.
- **Potentially Related** – There is some evidence to suggest a causal relationship (e.g., the event occurred within a reasonable time after administration of the trial medication). However, other factors may have contributed to the event (e.g., the participant's clinical condition, other concomitant events). Although an AE may rate only as "possibly related" soon after discovery, it can be flagged as requiring more information and later be upgraded to "probably related" or "definitely related", as appropriate.
- **Unlikely to be related** – A clinical event, including an abnormal laboratory test result, whose temporal relationship to study intervention administration makes a causal relationship improbable (e.g., the event did not occur within a reasonable time after administration of the study intervention) and in which other drugs or chemicals or underlying disease provides plausible explanations (e.g., the participant's clinical condition, other concomitant treatments).
- **Not Related** – The AE is completely independent of study intervention administration, and/or evidence exists that the event is definitely related to another etiology. There must be an alternative, definitive etiology documented by the clinician.]

